10.10.8.2. Patient-Report Outcomes for the SubStudy

Participants will complete PRO assessments at the relevant substudy visit prior to other clinical activities in the main study (eg, laboratory assessments). The PRO assessments should be checked for completeness by the study site staff before proceeding further with the substudy visit. Compliance with scheduled PRO activities will be monitored. Appropriately delegated site staff will oversee the administration of the PRO assessments at site visits to ensure protocol compliance, and will transcribe participant responses into the CRF.

10.10.8.2.1. HSS Pedi-FABS

The HSS Pedi-FABS is a validated 8-item instrument designed to quantify the activity level of children between 10 and 18 years of age over a 1 month recall period.²⁵ Participants will be asked to indicate the frequency and intensity of their athletic activity, level of play, and coach/trainer supervision.²⁶ The HSS Pedi-FABS should be completed as per the substudy Schedule of Activities (Section 10.10.2).

Two versions of the PRO will be completed; each regarding a different recall period:

- HSS Pedi-FABS (1 month recall)
- HSS Pedi-FABS (1 year recall)

If for whatever unanticipated reason a participant is unable to attend the site visit, the PRO assessments may be performed remotely in an acceptable manner if permissible by local guidelines/regulations. For example, if permissible, the PRO may be securely posted to the participant by courier for completion at home and the PRO can subsequently be collected the next time the participant attends the site or can be securely posted to site by courier.

10.10.9. Substudy AE Reporting

There are no additional specific requirements for non-serious AE reporting in the substudy. The requirements from the main protocol apply. Please refer to the Adverse Event Reporting section (Section 8.3) of the main protocol for further details.

10.10.9.1. Withdrawal From the Substudy Due to AEs

Participants who discontinue from the main study will also be discontinued from the substudy. An end of treatment visit will be performed per the main study protocol and participants should enter into the follow-up period, with an end of study visit scheduled for 4 weeks after the end of treatment visit.

Please refer to Section 7.1 of the main protocol for further details.

PFIZER CONFIDENTIAL

Page 108

10.10.10. Substudy Data Analysis/Statistical Methods

Detailed methodology for summary and statistical analyses of the data collected in this substudy will be described in a SAP, which will be maintained by the sponsor.

10.10.10.1. Sample Size Determination

Adolescent participants 12 to <18 years of age in the main study will be eligible for enrollment into the substudy.

10.10.10.2. Substudy Efficacy Analysis

There are no efficacy analyses planned for this substudy.

10.10.10.3. Substudy Safety Analyses

Bone safety findings as adjudicated by the safety adjudication committee will be summarized by treatment group using frequency and proportions along with 95% CI for the proportions. Further details will be specified in the SAP.

10.10.10.4. Substudy Interim Analysis

There will be no formal interim analysis for this substudy. The sponsor may conduct reviews of the data, including MRI data, during the course of the study for the purpose of safety assessment or to support regulatory submissions.

10.10.11. Substudy Safety Adjudication Committees

To help assess the specific, complex safety events in this substudy, a Safety Adjudication Committee consisting of clinical experts in the relevant clinical area will be established to harmonize and standardize assessments. In order to allow for an unbiased safety assessment, the members of these committees will be blinded to treatment assignment. Further information about the Safety Adjudication Committee can be found in the respective charter, including a specific description of the scope of their responsibilities, a plan in which communication timelines are defined, and the exact process and definition used by the committee to adjudicate the safety events that they will adjudicate. Other safety events for adjudication may be identified and included in the remit of the Safety Adjudication Committees as appropriate.

Appendix 4. References	

## PFIZER GENERAL BUSINESS

# **1. VERSION HISTORY**

Version/	Associated	Rationale	Specific Changes
Date	Amendment		
1	Original	N/A	N/A
18 Feb 2022	21 Dec 2021		
2	Amendment 1	Per India BoH's	Added SCORAD efficacy assessment for
12 May 2022	23 Mar 2022	recommendation	atopic dermatitis as a secondary endpoint. (Sections 2.1, 2.1.2, 3.2.3, 5.2.1, 6.2.3, Appendix 1, Appendix 2.4)
			Revised "abnormal developmental bone findings", "abnormal bone findings", "bone abnormalities" to "bone safety findings" in Sections 2.1, 2.1.3, 2.2, 3.3.1, 5.2.1, 6.3.1, Appendix 1.
			Removed text: "Photographic images of the lesion will be taken as part of source documentation, wherever possible." in Appendix 2.2 and Appendix 2.3 to align with Protocol Amendment 1.
			Added subset analysis based on monotherapy or combination therapy in Section 6.4.
3 13 Jul 2023	Amendment 1 23 Mar 2022	Add safety population	Added safety population and details for FAS in the analysis sets in Section 4.
			Changed the analysis population from FAS to Safety in Sections 3.1, 6.1.1, 6.6 and Appendix 1.
			Removed 'randomized' in Sections 6.5.1 and 6.5.2 as tables will be summarized according to actual treatment.

# Table 1.Summary of Changes

#### PFIZER GENERAL BUSINESS

# **2. INTRODUCTION**

This statistical analysis plan (SAP) provides the detailed methodology for summary and statistical analyses of the data collected in Study B7451094. This document may modify the plans outlined in the protocol; however, any major modifications of the primary endpoint definition or its analysis will also be reflected in a protocol amendment.

Objectives	Endpoints	Estimands
Primary:	Primary:	Primary:
• To evaluate the safety of abrocitinib in participants aged 12 years and older with moderate to severe Atopic Dermatitis (AD)	• Incidence of adverse events (AEs) and serious adverse events (SAEs)	• The primary estimand for safety is the incidence of AEs and SAEs in participants aged 12 years and older with moderate to severe AD, from the time of first dose to Week 16, regardless of dosing compliance or treatment discontinuation.
Secondary:	Secondary:	Secondary:
• To assess the efficacy of abrocitinib in participants aged 12 years and older with moderate to severe AD	
 
Response based on Investigator's Global Assessment (IGA) score of clear (0) or almost clear (1) and greater than or equal to 2 points improvement from baseline at Week 12
 
Response based on achieving ≥75% improvement from baseline in the Eczema Area and Severity Index total score (EASI-75) at Week 12
 
Response based on ≥75% improvement in Scoring Atopic Dermatitis total score (SCORAD75) at week 12
 
	• The secondary estimand is the treatment effect of abrocitinib on participants aged 12 years and older with moderate to severe AD, based on IGA response, EASI-75 response and SCORAD75 response from baseline to Week 12, considering patients who discontinued treatment as non-responders and based on outcome measures of POEM and ADCT from baseline to Week 12 and at all scheduled time points. Data collected after treatment discontinuation is excluded.

## 2.1. Study Objectives, Endpoints, and Estimands

PFIZER GENERAL BUSINESS

	
 
Change from baseline in Patient-Oriented Eczema Measure (POEM) at Week 12 and at all scheduled time points
 
Change from baseline in Atopic Dermatitis Control Tool (ADCT) at Week 12 and at all
 
	
Primary substudy	Primary substudy	Primary substudy estimand(s).
objective(s):	endnoints (as secondary	Timary substudy comand(s).
o.jeen (c).	endpoints for B7451094):	
• To evaluate the potential	• The incidence of bone	• The primary substudy
effects of abrocitinib on	safety findings in knee	estimand is the incidence of
bone development in	MRI 1 year after	bone safety findings in knee
adolescent participants 12	randomization in	MRI after 1 year of being
to <18 years of age, as	adolescent participants	exposed to abrocitinib in
assessed by knee	exposed to abrocitinib	adolescent participants 12 to
magnetic resonance	100 mg and 200 mg once	<18 years of age, regardless of
imaging (MRI).	daily (OD).	dosing compliance or
		accurg compliance of

# 2.1.1. Primary Estimand(s)

The primary estimand is the incidence of AE/SAE regardless of whether an intercurrent event occurs. The estimand is defined according to the primary objective and is in alignment with the primary endpoint. It includes the following 4 attributes:

- Population: Patients aged 12 years and older with moderate to severe AD, as defined by the inclusion and exclusion criteria, and who are randomized;
- Variable: Binary indicator of whether any AE/SAE occurred at least once;
- Intercurrent event(s): Dosing compliance or treatment discontinuation is not considered for analysis. All data collected (including data after discontinuation of treatment) are included.
- Population-level summary: Incidence rate of AEs/SAEs, defined as the number of participants with AEs/SAEs from the time of first dose to Week 16 divided by the number of participants, in each treatment arm.

## PFIZER GENERAL BUSINESS

## 2.1.2. Secondary Estimand(s)

The secondary estimand 1 is the treatment effect of abrocitinib based on IGA response. This estimand is defined according to the secondary objective and in alignment with the secondary endpoint response based on IGA score. It includes the following 4 attributes:

- Population: Patients aged 12 years and older with moderate to severe AD, as defined by the inclusion and exclusion criteria, and who are randomized;
- Variable: Response based on IGA score of clear (0) or almost clear (1) and greater than or equal to 2 points improvement from baseline at Week 12; participants who discontinued intervention for any reason or required a rescue medication are considered as non-responders;
- Intercurrent event: The intercurrent event "intervention discontinuation for any reason" is addressed in the variable definition;
- Population-level summary: IGA response rate with 95% confidence interval (CI), in each treatment arm.

The secondary estimand 2 is the treatment effect of abrocitinib based on EASI-75 response. This estimand is defined according to the secondary objective and in alignment with the secondary endpoint response based on EASI-75. It includes the following 4 attributes:

- Population: Patients aged 12 years and older with moderate to severe AD, as defined by the inclusion and exclusion criteria, and who are randomized;
- Variable: Response based on improvement of ≥75% from baseline EASI score at Week 12; participants who discontinued intervention for any reason or required a rescue medication are considered as non-responders;
- Intercurrent event: The intercurrent event "intervention discontinuation for any reason" is addressed in the variable definition;
- Population-level summary: EASI-75 response rate with 95% CI, in each treatment arm.

The secondary estimand 3 is the treatment effect of abrocitinib based on SCORAD75 response. This estimand is defined according to the secondary objective and in alignment with the secondary endpoint response based on SCORAD75. It includes the following 4 attributes:

• Population: Patients aged 12 years and older with moderate to severe AD, as defined by the inclusion and exclusion criteria, and who are randomized;

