 - In the opinion of the investigator or Pfizer (or designee) exclusion is required.

Prior/Concomitant Therapy:

- 8. Prior treatment with systemic JAK inhibitors.
- 9. Participants who are vaccinated with live attenuated vaccine within the 6 weeks prior to the first dose of abrocitinib or who are expected to be vaccinated with these vaccines during treatment or during the 6 weeks following discontinuation of abrocitinib.

10. Have received any of the following treatment regimens specified in the timeframes outlined below:

Within 1 year of first dose of study intervention:

• Prior treatment with non B cell-specific lymphocyte depleting agents/therapies (eg, alkylating agents [eg, cyclophosphamide or chlorambucil], total lymphoid irradiation, etc.). Participants who have received rituximab or other selective B lymphocyte depleting agents (including experimental agents) are eligible if they have not received such therapy for at least 1 year prior to study baseline and have normal CD 19/20+ counts by FACS analysis.

Within 12 weeks of first dose of study intervention:

• Biologic drugs that have immunomodulatory properties or could be used to treat AD: within 12 weeks of first dose of investigational product or 5 half-lives (if known), whichever is longer.

Other biologics without immunomodulatory properties (eg, insulin) are permissible at the judgement of the Investigator.

Within 4 weeks of first dose of study intervention:

 Use of oral immunosuppressive drugs (eg, CsA, azathioprine, methotrexate, systemic corticosteroids, mycophenolate-mofetil, IFN-γ) within 4 weeks of first dose of study intervention or within 5 half-lives (if known), whichever is longer.

NOTE: Systemic corticosteroids must be discontinued before Study Day 1, but a specific timeframe for discontinuation prior to first dose of abrocitinib is not required.

NOTE: Corticosteroid inhalers and intranasal sprays are permissible.

NOTE: Ophthalmic corticosteroids are permissible.

Within 1 week of first dose of study intervention:

• Anti-platelet drugs.

Note: low dose acetyl salicylic acid (<100 mg QD) is permitted, for the purpose of cardiovascular prophylaxis, at the discretion of the investigator.

11. Require treatment with prohibited concomitant medication(s) or have received a prohibited concomitant medication.

Prior/Concurrent Clinical Study Experience:

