6.8.2. Prohibited Medications and Treatments

Participants are required to discontinue and avoid using certain medications and treatments (refer to Inclusion Criteria [Section 5.1], Exclusion Criteria [Section 5.2], and Appendix 7). Participants should be instructed at each visit to contact the study site investigator promptly if there are any intended changes or additions to concomitant medications.

Participants who received prior treatment with systemic JAK inhibitors are to be excluded from the study. Prior treatment with topical JAK inhibitors is not exclusionary.

Restrictions on certain vaccinations are described in Section 5.3.3.

The Pfizer study team is to be notified of any prohibited medications taken during the study. After consulting with the Pfizer medical monitor, the investigator will make a judgement on the ongoing eligibility of any participant with prohibited medication use during the study.

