6.8.3. Rescue Medicine

After Week 4 if medically necessary, participants with intolerable AD symptoms may receive locally-approved rescue therapy with systemic corticosteroids for up to 14 days at a time, at the investigator's discretion, according to local product label. Participants receiving systemic rescue therapy may continue to receive abrocitinib concurrently and should

continue study visits and assessments. Rescue therapy will be obtained locally and administration must be recorded on the CRF. As possible, investigators should conduct safety and efficacy assessments (eg, safety labs, disease severity scores) before administering rescue therapy. An unscheduled visit may be used for this purpose, if necessary.

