9.1.1.2. Secondary Estimands

The secondary estimand 1 is defined by the following attributes:

Population: Patients aged 12 years and older with moderate to severe AD.

Variable: Response based on IGA score of clear (0) or almost clear (1) and greater than or equal to 2 points improvement from baseline at Week 12; participants who discontinued intervention for any reason are considered as non-responders.

Treatment condition: The randomized intervention.

The intercurrent event "intervention discontinuation for any reason" is addressed in the variable definition.

Population-level summary: IGA response rate with 95% CI, in each treatment arm.

The secondary estimand 2 is defined by the following attributes:

Population: Patients aged 12 years and older with moderate to severe AD.

Variable: Response based on improvement of \geq 75% from baseline EASI score at Week 12; participants who discontinued intervention for any reason are considered as non-responders.

Treatment condition: The randomized intervention.

The intercurrent event "intervention discontinuation for any reason" is addressed in the variable definition.

Population-level summary: EASI-75 response rate with 95% CI, in each treatment arm.

The secondary estimand 3 is defined by the following attributes:

Population: Patients aged 12 years and older with moderate to severe AD.

Variable: Response based on improvement of \geq 75% in SCORAD from baseline at Week 12; participants who discontinued intervention for any reason are considered as non-responders.

PFIZER CONFIDENTIAL

Treatment condition: The randomized intervention.

The intercurrent event "intervention discontinuation for any reason" is addressed in the variable definition.

Population-level summary: SCORAD75 response rate with 95% CI, in each treatment arm.

The secondary estimand 4, is defined by the following attributes:

Population: Patients aged 12 years and older with moderate to severe AD.

Variable: Change from baseline in POEM at Week 12 and at all scheduled timepoints; data after treatment discontinuation at any time during the treatment period will be censored.

Treatment condition: The randomized intervention. The intercurrent event "intervention discontinuation for any reason" is addressed in the variable definition.

Population-level summary: Mean and standard deviation.

The secondary estimand 5 is defined by the following attributes:

Population: Patients aged 12 years and older with moderate to severe AD.

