#### PFIZER GENERAL BUSINESS

## 6.2. Secondary Endpoint(s)

#### 6.2.1. Response based on IGA Score

- Estimand strategy: Composite (Section 2.1.2).
- Analysis set: FAS (Section 4).
- Analysis methodology: Descriptive statistics and 95% CIs.
- Intercurrent events and missing data: Missing data due to participant discontinuing treatment or from the study for any reason are considered non-response. In addition, participants who required a rescue medication are considered non-responders.
- The response rate along with the 95% CI will be estimated for each treatment arm. In addition, summary of IGA scores for all scheduled time points will be presented for each treatment arm.

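### The SAP's non-response and censoring rules cover only discontinuation and rescue, so a participant kept on abrocitinib after other AD-active systemic therapy or phototherapy can be counted as a Week 12 responder

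*SAP*

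**What the plan says.** **Analysis rules.** For IGA, EASI-75 and SCORAD75, the variable definition in SAP 2.1.2 states that "participants who discontinued intervention for any reason or required a rescue medication are considered as non-responders". SAP 6.2.1 to 6.2.3 repeat this in two sentences: "Missing data due to participant discontinuing treatment or from the study for any reason are considered non-response", and "In addition, participants who required a rescue medication are considered non-responders". For POEM and ADCT (SAP 2.1.2, 6.2.4, 6.2.5), values after discontinuation or rescue are censored. Appendix 1 names no further event. The intercurrent-event attribute of estimands 1 to 5 lists discontinuation only, although the variable adds rescue. Protocol 9.1.1.2 is narrower still for the response endpoints: "participants who discontinued intervention for any reason are considered as non-responders".

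**What rescue means.** The SAP gives no definition. Protocol 6.8.3 says that, after Week 4, "participants with intolerable AD symptoms may receive locally-approved rescue therapy with systemic corticosteroids for up to 14 days at a time", and that abrocitinib may continue.

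**Other AD-active treatment.** Exclusion criterion 10 (protocol 5.2) lists oral immunosuppressants such as ciclosporin, azathioprine and methotrexate, and "Biologic drugs that have immunomodulatory properties or could be used to treat AD". Criterion 8 excludes prior systemic JAK inhibitors. Protocol 6.8.2 carries the exclusion criteria into the treatment period. If a prohibited drug is used, the study team is notified and, after consultation with the medical monitor, "the investigator will make a judgement on the ongoing eligibility of any participant with prohibited medication use during the study". Appendix 7 has a similar provision. Protocol 7.1 does not list prohibited medication among the reasons for stopping study intervention. Phototherapy is not named in 5.2, 6.8.1 to 6.8.3 or Appendix 7.

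**The concern.** SAP 6.2.1 to 6.2.3 call the strategy composite. Needing rescue counts as failure even when the skin has cleared by Week 12. The evident purpose is to keep clearance reached with added systemic treatment from being credited to abrocitinib, although the SAP does not say so. The rule achieves this for one drug class in one time window. Two participants who both needed systemic help for AD, both stayed on abrocitinib and both reached IGA 1 can be scored in opposite ways, depending on which treatment was added.

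A misclassification of this kind can only raise a response rate. For POEM and ADCT, scores recorded under the added therapy stay in the abrocitinib mean. These are the study's efficacy outputs, and SAP 7 provides for interim efficacy summaries to the Indian authority. Because the study is open-label, a decision on such cases made during analysis would be made with the dose known. A rule fixed in advance avoids that.

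**Working it through.** **The plan's own figure.** Protocol 9.5 gives a maximum margin of error of 10% for an AE incidence with 100 per arm. At 95% with the normal approximation: 1.96 × √(0.5 × 0.5 / 100) = 0.098, or 9.8 points. It reproduces. It concerns precision and does not bear on the classification rule.

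**Applying the rule to cases.** Inclusion requires IGA of at least 3 at baseline, so IGA 1 at Week 12 is a fall of at least 2 points. Every case below has IGA 1 at Week 12, and no other trigger applies.

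| Added AD treatment | Abrocitinib | Rescue under 6.8.3? | SAP result |
|---|---|---|---|
| Systemic corticosteroid, Week 5 | continued | yes | non-responder |
| Ciclosporin, from Week 5 | continued | no | responder |
| Ciclosporin, from Week 5 | stopped | no | non-responder (discontinuation) |
| Systemic corticosteroid, Week 3 | continued | no (before the 6.8.3 window) | undefined; responder if 6.8.3 is the definition |
| Phototherapy, Week 6 | continued | no | responder |

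**Whether another provision catches rows 2, 4 and 5.**
- SAP 4 defines no per-protocol set.
- SAP 6.4 splits participants by permitted concomitant AD therapies, so prohibited therapy is not addressed.
- SAP 6.5.4 summarises concomitant drug and non-drug treatments by arm. This makes use visible but reclassifies nobody.
- The SAP plans no sensitivity analysis for prohibited therapy.

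**Size per case.** Let x be the responders under the SAP rule, n = 100 (protocol 9.5), and k the number of those responders who used such therapy and stayed on abrocitinib. The corrected rate is (x − k)/n, and the interval is p ± 1.96 × √(p(1 − p)/n), the method in SAP 5.2.1. Each case moves the rate by 1/100, or 1 point.

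For scale, take the B7451012 IGA rates in protocol 2.2.2, 43.8% (200 mg) and 23.7% (100 mg), rounded to 44/100 and 24/100. The documents give no value for k; 0 to 10 is an assumed range. Example for k = 3, 200 mg: (44 − 3)/100 = 41%; 1.96 × √(0.41 × 0.59/100) = 9.6 points; interval 31.4 to 50.6.

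| k (assumed) | 200 mg, % (95% CI) | 100 mg, % (95% CI) |
|---|---|---|
| 0 | 44 (34.3–53.7) | 24 (15.6–32.4) |
| 1 | 43 (33.3–52.7) | 23 (14.8–31.2) |
| 3 | 41 (31.4–50.6) | 21 (13.0–29.0) |
| 5 | 39 (29.4–48.6) | 19 (11.3–26.7) |
| 10 | 34 (24.7–43.3) | 14 (7.2–20.8) |

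Up to k = 5 the corrected rate stays inside the unadjusted interval. At k = 10 it falls just outside in both arms.

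**The case against.** The strongest reply is that these cases are deviations. Oral immunosuppressants and AD biologics are restricted through protocol 6.8.2 and 5.2, the study team must be told, and the medical monitor is consulted before anyone continues. The systemic escalation that the protocol offers is rescue, and rescue is counted. Phototherapy is not among the permitted AD therapies in 6.8.1. Anyone taken off abrocitinib is already a non-responder. Several conditions must therefore coincide before a case is misclassified. This stands: it limits the likely number of cases but does not close the gap, because 6.8.2 foresees continued participation and 7.1 does not require stopping.

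A second reply is that the SAP's undefined term could be read broadly, so that any systemic treatment for uncontrolled AD is coded as rescue. That is possible, but the only description in either document is the one in 6.8.3, and a broad reading would have to be settled at analysis.

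A reader might go further in three ways that the documents do not support:
- *That response rates are biased upward, or biased more at one dose.* No rate of use is given, overall or by arm. With no such users the bias is zero.
- *That the investigator may freely choose between a counted and an uncounted drug.* The notification and consultation steps in 6.8.2 say otherwise.
- *That the effect should be judged against the 9.7-point IGA difference between doses quoted for B7451013.* SAP 5.1 plans no hypothesis test and estimates each arm separately.

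**Conclusion.** The gap is real and is more than a missing detail: followed as written, the rule can score a response after other AD-active systemic therapy or phototherapy when a rescue steroid course would have scored failure. The conclusion requires that the participant stays on study intervention, not only on study, and meets the Week 12 criterion. It also takes protocol 6.8.3 as the meaning of rescue.

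The size is about 1 percentage point of overstatement per such participant in an arm of 100. The total cannot be derived from the documents. The affected endpoints are secondary and descriptive, and the primary safety endpoint is untouched. This is a modest correction worth making before the data are analysed.

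A reader might infer that any systemic corticosteroid at any time should count as failure. That does not follow. Adolescents are treated for up to 1 year (protocol 10.10.6), so without a cut-off a course after Week 12 would reverse a Week 12 response. A course for a condition other than AD is not AD treatment failure.

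**What to change.** In SAP 2.1.2 (both the variable and the intercurrent-event attributes, estimands 1 to 5), 6.2.1 to 6.2.5 and Appendix 1:

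1. Define rescue medication by reference to protocol 6.8.3.
2. Add an intercurrent event: use, after first dose and before the Week 12 assessment, of any other systemic therapy given for AD (systemic corticosteroid, oral immunosuppressant, AD biologic, non-study systemic JAK inhibitor) or of phototherapy.
3. Handle it as non-response for IGA, EASI-75 and SCORAD75. For POEM and ADCT, censor data from the start of that therapy.
4. Identify cases from the concomitant drug and non-drug treatment records, using a coded list fixed before database lock.
5. Align the estimands in protocol 9.1.1.2, which currently omit rescue as well.

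This is an analysis rule only and changes no treatment rule. The cost is SAP and protocol wording plus a coded list. Protocol 6.8 already requires concomitant medications and treatments to be queried at each visit, and SAP 6.5.4 already summarises them. The downside is that response rates may be slightly lower; if no such use occurs, they do not change.
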